8.5.1 Procedure for Limited Physical Examination in BESS

Participants in BESS are unwell and may be haemodynamically unstable. Handling of the participants, including full physical examination, is minimised in standard care, as per current NICE guidance (42).

All participants must have a physical examination before and after each administration of the trial intervention. This is a limited physical examination to minimise any disturbance to the infant participant.

Examinations must be carried out any time in the period 2 hours prior to each administration, and the interval of time between 1 hour and 2 hours post each administration. The post administration examination is deliberately delayed by at least one hour after administration to allow stabilisation of the participants' vital signs and avoid prolonging the handling associated with administration. The limited examination must include the following:

- Temperature
- Heart rate
- Blood pressure
- Respiratory rate
- Oxygen saturations (peripheral)

To minimise handling, if a participant has had a full physical examination as part of standard care at any time in the period 2 hours prior to the administration and the vital signs data have been collected, then this examination should be counted as their BESS physical examination and the vital sign data used.

The physical examination vital sign data must be recorded in the patient notes and transcribed onto the relevant BESS CRF.

8.6 Other Assessments

8.6.1 Parent Reported Quality of Life questionnaires

The parent reported outcome measure the Liverpool Respiratory Symptom Questionnaire (LRSQ), is a web-accessible questionnaire that has been optimised for many platforms

IRAS 220853 Page **40** of **87**

including smart-phones. Links to the form will be emailed to parents prior to the intended completion dates (in all three seasons at 6m, and in addition at 12m to parents of infants recruited in seasons 1 and 2). A paper version is available with a "free-post" return envelope.

8.6.2 Special Assays or Procedures

8.6.2.1 Collection & processing of BAL fluid

BAL sampling with 0.9% sodium chloride (2x1mL/kg) will be done for all participants immediately prior to intervention, at 24hrs post intervention and repeated daily while the infant remains on MV (see Table 2).

Both tracheal toilet and BAL sampling is done by catheter access to the trachea via the endotracheal suction port without disconnecting the infant from the ventilator or by disconnecting the infant from the ventilator and performing hand bagging while accessing the trachea via a side-port with one-way valve.

8.6.2.2 Blood gas sampling

Blood Gas sampling is a routine procedure required for the clinical monitoring of all people requiring mechanical ventilation. The typical sample volume of blood drawn from infants and children is 100 microliters equivalent to two drops. Infants and children can have Blood Gas sampling by drawing blood from an existing arterial line or from a heel prick. To minimise disturbance and risks to infants from additional research procedures, the data from routine Blood Gas samples will be used for the trial when collected within a 2-hour window of the scheduled trial Blood Gas sample timepoint up to and including the sample due at 48 hours post first intervention (see Table 2). After 48 hours, i.e. day 3 and onwards, and only if the infant continues to require mechanical ventilation, then data from any one routine blood gas sample collected within a 6-hour window 9:00am to 3:00pm in each subsequent 24-hour interval will be collected (the first such sample if more than one is taken). A research Blood Gas sample will only be done if a routine blood gas sample is not done or planned within each 24-hour period sampling window.

Blood gas machines are usually kept in the PICU rather than the hospital/Trust laboratory. PICUs will not be CPS accredited but each Trust laboratory, and the machinery they are responsible for, will be. The CTRC will acquire a copy of the trust CPS laboratory certificate and calibration log for the blood gas machines as part of the compulsory 'Green Light Checklist' procedures before a site can open to recruitment. The Trust laboratory **must** take responsibility for service of the PICU blood gas machines and be able to provide a quality control log for maintenance and calibration of each blood gas machine.

8.6.2.3 Additional samples (WP-C at Liverpool and Southampton only)

Participants at Liverpool and Southampton will be given the option to consent to a single intravenous dose of D₉-labelled choline which will inform the mechanistic sub-study on surfactant synthesis and metabolism (WP-C; see section 12.2 for full details). This work will not inform either the primary or secondary outcomes of the main trial (WP-A). These samples will **only** be taken from participants who have provided specific consent for this optional additional work.

IRAS 220853 Page **41** of **87**

Small volume lung lavages will be collected immediately prior to intervention and at 24hrs, as per the standard follow-up (see section 8.2), and at additional time points of 12hrs and 36hrs for WP-C participants only. Samples of 1.25mL (range 1.0 to 1.3mL) of blood will be collected at the same time points for WP-C participants at Liverpool and Southampton only.

8.7 Patient Transfer and Withdrawal

8.7.1 Patient Transfers

It is very unlikely that participants taking part in BESS will be transferred during their trial treatment, given the severity of illness of participants and the short time period for administration of the intervention. In the unlikely scenario that a BESS participant is transferred while they remain intubated, their trial treatment will end at transfer unless they are transferred directly to another BESS site. For participants transferred to another participating trial site the receiving trial site must take over responsibility for the participant.

A copy of the participant CRFs should be provided to the new site. The parent will have to sign a new consent form at the new site, and until this occurs, the participant remains the responsibility of the original site.

If a participant is transferred to a site that is not taking part in BESS then they will be withdrawn from the trial and will receive no further interventions. Their care will revert to the standard practice and will not be affected by the withdrawal from the trial. The CTRC should be notified in writing of all participant transfers, whether or not to a participating trial site.

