8.7.2 Withdrawal from the Trial

In consenting to the trial, parents are consenting to trial intervention and treatment, follow-up assessments and data collection for their child.

The rights and welfare of the participants will be protected by emphasising to their parents that the quality of medical care will not be adversely affected if they withdraw consent for their child to participate in this trial.

8.7.2.1 Partial Withdrawal from Trial (Intervention and Treatment), allowing Follow-up and Data Collection)

Participants may be withdrawn from trial intervention and treatment for any of the following reasons:

- a. Parent withdraws consent.
- b. Unacceptable toxicity.
- c. Intercurrent illness preventing further treatment.
- d. Any change in the participant's condition that justifies the discontinuation of treatment in the clinician's opinion.

If voluntary withdrawal from trial intervention and treatment occurs, the parent should be asked to allow continuation of scheduled evaluations (follow-up and data collection) and be given appropriate

IRAS 220853 Page **42** of **87**

care under medical supervision until the symptoms of any adverse event resolve or the participant's condition becomes stable.

If a parent wishes to withdraw their infant from trial intervention and treatment, sites should explain the importance of remaining on trial follow-up, or failing this, of allowing routine follow-up data to be used for trial purposes. Follow-up and data collection will continue unless the parent explicitly withdraws consent for follow-up or data collection. Research data obtained up to the point of withdrawal of consent will be retained, and further data will only be collected where required by law for reporting to regulatory agencies (i.e. serious adverse events). Research samples will be destroyed or retained for the purpose of the trial according to the wishes of the parent.

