8.7.2.2 Withdrawal from Trial Completely

Parents are free to withdraw consent at any time without providing a reason. Parents who wish to withdraw consent for the trial completely (trial intervention, follow-up and data collection) will be informed that pseudo-anonymised data collected up to the point of that withdrawal of consent will be included in the analyses, in accordance with current data protection legislation. The participant will not contribute further data to the trial (with the exception of serious adverse event data); the CTRC should be informed in writing and a Withdrawal CRF should be completed. Data up to the time of withdrawal will be included in the analyses.

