8.8 Loss to Follow-up

Trial follow-up will be in part via routinely collected data downloaded in a bespoke trial download by each recruiting site; in part via paper CRFs completed by the trial RNs and RPTs; and in part via LRSQs collecting Parent Reported Outcome Measures (PROMs) at 6 and 12 months post randomisation. Where a patient is lost to follow-up before the relevant time point (e.g. lost due to transfer to another hospital), contact will initially be attempted by the trial RNs and the PI at each site. Wherever possible, information on the reason for loss to follow-up will be recorded.

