# 8.4.3. Removal of patients from therapy or assessment

Participants may be withdrawn from trial intervention for any of the following reasons:

- Parent withdraws consent
- Unacceptable toxicity
- Intercurrent illness preventing further treatment
- Any change in the participant's condition that justifies the discontinuation of treatment in the clinician's opinion.

# Form prepared: 16/04/2024 v2.0 for BESS Page 10 of 30

Follow-up and data collection will continue unless the parent explicitly withdraws consent. Research samples will be destroyed or retained for the purpose of the trial according to the wishes of the parent.

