## 18. Missing data and withdrawals

Missing data will be quantified for all outcomes presented in the final analysis report. Where known, reasons for missingness will be given.

Withdrawals from trial will be summarised and presented as line listings detailing:

- 1. Site
- 2. Time from randomisation to withdrawal
- 3. Decision to withdraw participant made by:
  - a. Clinician
  - b. Parent/person with parental responsibility
  - c. Both clinician and parent/person with parental responsibility
- 4. Reason for withdrawal:
  - a. Death
  - b. Lost to follow-up
  - c. Transfer to non-participating site
  - d. Withdrawal of consent for follow-up
  - e. Other (specify)

Every effort will be made to collect follow-up data even in the event of participants discontinuing the trial intervention. In the case of withdrawals from study, available data will still be included using an intent-to-treat approach.

#### 19. Additional analyses Additional analysis 1

A sensitivity analysis of the primary analysis will be done to assess the robustness of the primary analysis. This will be done using a Cox proportional hazards model and will allow the censoring of patients who do not observe the primary endpoint of successful extubation. The start-point and end point for patients having the event of successful extubation will be the same as those defined in section 17.4.1.1. For patients who do not have a successful extubation recorded these will be censored at the last date and time (OAODATXD) an observation is recorded on the Observations and Outcomes CRF. The cox proportional hazards model will include the allocated treatment and time on ventilation prior to randomisation as covariates.

#### Additional analysis 2

A subgroup analysis of the primary outcome will be undertaken, This was based on a recommendation from the Trial Steering Committee who met on the 20th February 2024.

The subgroup analysis will examine the primary outcome stratified by whether the baby was born prematurely or not and will include an interaction term between treatment and prematurity in the linear mixed effect model described in 18.4.1.2.

Results will be presented from the model with the interaction result alongside.

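### Protocol 8.7.1 withdraws from the trial an infant moved to a non-BESS site, which conflicts with the rules that follow-up stops only when a parent withdraws consent

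*Protocol*

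**What the plan says.** Protocol 8.7.1 opens on transfer during the dosing period: "It is very unlikely that participants taking part in BESS will be transferred during their trial treatment". It then gives a rule for infants who still have a tube in place: "In the unlikely scenario that a BESS participant is transferred while they remain intubated, their trial treatment will end at transfer", with an exception for a direct move to another BESS site. A later paragraph adds: "If a participant is transferred to a site that is not taking part in BESS then they will be withdrawn from the trial". That sentence goes on to say that no more interventions are given, and the next one returns the infant to standard care.

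SAP 18 lists reasons for withdrawal from the trial. One is "Transfer to non-participating site"; withdrawal of consent for follow-up is a separate entry.

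Three other places point the other way:

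- Protocol 8.7.2.1, on stopping the intervention: "Follow-up and data collection will continue unless the parent explicitly withdraws consent for follow-up or data collection".
- SAP 8.4.3: "Follow-up and data collection will continue unless the parent explicitly withdraws consent".
- Protocol 8.8 treats a move as a loss that sites try to recover. It begins "Where a patient is lost to follow-up before the relevant time point (e.g. lost due to transfer to another hospital" and then has the research nurses and the PI attempt contact.

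Protocol 8.7.2.2 says what complete withdrawal means for data: "The participant will not contribute further data to the trial (with the exception of serious adverse event data". It is written for parents who withdraw consent.

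**The concern.** The protocol separates stopping the intervention from leaving the trial. The transfer sentence in 8.7.1 uses the second term for an event that is not a parental decision. A site that follows it literally could stop collecting data on a randomised infant whose parent agreed to follow-up and never withdrew.

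The event comes after randomisation, and its timing may depend on how quickly the infant recovers, which treatment could change. SAP 17.1 analyses only infants with the outcome observed and makes no imputation. Losses through transfer would therefore simply leave the comparison, and they could be informative.

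**Working it through.** **1. Rules side by side, for an infant moved to a non-BESS hospital with no withdrawal of consent**

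| Place | Intervention | Follow-up and data |
|---|---|---|
| Protocol 8.7.1, intubated-transfer sentence | ends, unless moved directly to a BESS site | not addressed |
| Protocol 8.7.1, non-BESS sentence | none further | withdrawn from trial; effect on data not defined |
| Protocol 8.7.2.1 and SAP 8.4.3 | may be stopped | continue unless the parent explicitly withdraws |
| Protocol 8.8 | not addressed | site attempts contact |
| SAP 18 | not addressed | coded as trial withdrawal, apart from consent withdrawal |

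The places agree that no further trial doses are given at a non-BESS hospital. They disagree on whether the infant stays in follow-up. No passage settles that for an infant transferred after extubation.

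**2. Two readings of 8.7.1**

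*Narrow: only infants still in the treatment period.* The conflict remains, because the infant leaves the trial without parental withdrawal. If the infant is moved while intubated, final extubation may not be recorded. SAP 17.4.1.2 then leaves the infant out of the complete-case primary analysis, and the Cox sensitivity analysis in SAP 19 censors at the last recorded observation.

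*Literal: any transfer, including step-down after extubation.* The primary outcome is then usually already known. The exception is re-intubation elsewhere within the 48 hours that define a failed extubation (SAP 17.4.1).

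**3. Outcomes exposed under the literal reading**

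- At risk: end of oxygen and of NIV (SAP 17.4.5, 17.4.7), post-extubation SF ratio (17.4.4), hospital stay (17.4.8), 90-day status and readmission (17.5.6, 17.5.3), and LRSQ (17.4.9).
- Normally already observed: failed administration, air leak before PICU discharge, tube replacement before successful extubation, and death in PICU.

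A linked gap is that SAP 17.4.8.1 ends hospital stay at hospital discharge without saying whether an inter-hospital transfer counts.

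**4. Arithmetic**

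The plan's own figure first, with inputs from Protocol 11.3: means 4.83 and 4.08 days, SD 2.5 in both arms, two-sided alpha 0.05.

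- Log-scale variances, ln(1 + κ²): 0.2374 for κ = 0.518 and 0.3188 for κ = 0.613; sum 0.5562.
- Difference in log means: ln(4.08/4.83) − ½(0.3188 − 0.2374) = −0.2095.
- n per group = (z₀.₉₇₅ + z_power)² × 0.5562 / 0.2095² = 99.5, so 100 for 80% power; and 133.2, so 134 for 90% power.
- Dropout: 134/0.95 = 141.05, so 142 per group and 284 in all.

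This matches the protocol exactly. The 5% allowance is about 0.05 × 284 = 14 infants and belongs to the primary outcome.

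For a later outcome, let L be the **assumed** share missing through transfer. The number observed is 284(1 − L), and the confidence interval widens by 1/√(1 − L):

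| L (assumed) | Observed of 284 | CI width |
|---|---|---|
| 5% | 270 | ×1.03 |
| 10% | 256 | ×1.05 |
| 20% | 227 | ×1.12 |
| 30% | 199 | ×1.20 |
| 50% | 142 | ×1.41 |

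This is precision only, with equal loss in both arms. It does not measure bias. The 12-month LRSQ starts from fewer infants, because season 3 has no 12-month form.

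For the primary outcome, power is Φ(0.2095/√(0.5562/n) − 1.96) with n = 142(1 − L). It is 90.4% at 5% total loss, 88.8% at 10% and 84.9% at 20%. Only losses before final extubation is known count here, and the protocol expects such transfers to be very unlikely.

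**The case against.** The best reply is context. Section 8.7.1 starts with transfer during treatment, and the disputed sentence goes on to rule out further interventions and restore standard care. Those words fit an infant who could still be dosed. They say little to an extubated infant going to a local ward. The only text that ends data collection, in 8.7.2.2, concerns parents who withdraw consent. Protocol 8.8 provides for contact after a transfer. SAP 18 promises effort to collect follow-up after the intervention stops and keeps the available data of infants who are withdrawn; its transfer entry is a line-listing category, not an instruction to stop.

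Much of this stands. A reader might infer that every infant stepped down after extubation loses all later outcomes. The documents do not say so: it follows only from the literal reading, and 8.8 partly counters it. A reader might also infer that all safety comparisons are affected, but most safety outcomes are complete before PICU discharge. Some routes do not depend on where the infant is. LRSQ links are sent centrally (Protocol 14.4), readmission is parent-reported, and PICANet data run to 90 days (Protocol 8.2). Central sending is documented only for the LRSQ, however, and 90-day mortality rests on a local enquiry of the hospital record (Protocol 8.4.2).

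Context does not remove the conflict. On the narrow reading the sentence still withdraws an infant without parental withdrawal, and SAP 18 still codes that as leaving the trial.

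**Conclusion.** The inconsistency is real and should be resolved. Protocol 8.7.1 and SAP 18 make transfer to a non-BESS site a trial withdrawal. Protocol 8.7.2.1, Protocol 8.8 and SAP 8.4.3 do not let follow-up end that way.

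Its size is unknown. With about 14 tertiary PICUs recruiting and some infants arriving already intubated, later step-down elsewhere is foreseeable, but the documents give no rate. The shares in the table are assumptions. Setting them against the 5% dropout allowance would mislead, because that allowance was made for the primary outcome. Informative loss is a possibility that rests on transfer timing depending on recovery; the documents do not establish it.

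The protocol supplied ends its amendment log at version 2.0, while the SAP cites versions 3.0 and 6.0. The sentence may since have been changed.

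**What to change.** First check 8.7.1 in the current protocol. If the sentence stands:

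- **Protocol 8.7.1:** reconcile it with 8.7.2.1, 8.8 and SAP 8.4.3. State that transfer to a non-BESS site ends participation only as regards the trial intervention, and that follow-up and data collection continue unless the parent withdraws consent. The existing rule on further doses is left as it is.
- **SAP 18:** record such transfers as discontinuation of intervention, where any was still due, and not as trial withdrawal.
- **SAP 17.4.8.1:** state that an inter-hospital transfer is not a hospital discharge.

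The cost is a few sentences, plus occasional contact by existing site staff with the receiving hospital for dates of stopping support and of discharge. Clinical care does not change.

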8.7.2 Withdrawal from the Trial

In consenting to the trial, parents are consenting to trial intervention and treatment, follow-up assessments and data collection for their child.

The rights and welfare of the participants will be protected by emphasising to their parents that the quality of medical care will not be adversely affected if they withdraw consent for their child to participate in this trial.

8.7.2.1 Partial Withdrawal from Trial (Intervention and Treatment), allowing Follow-up and Data Collection)

Participants may be withdrawn from trial intervention and treatment for any of the following reasons:

- a. Parent withdraws consent.
- b. Unacceptable toxicity.
- c. Intercurrent illness preventing further treatment.
- d. Any change in the participant's condition that justifies the discontinuation of treatment in the clinician's opinion.

If voluntary withdrawal from trial intervention and treatment occurs, the parent should be asked to allow continuation of scheduled evaluations (follow-up and data collection) and be given appropriate

IRAS 220853 Page **42** of **87**

care under medical supervision until the symptoms of any adverse event resolve or the participant's condition becomes stable.

If a parent wishes to withdraw their infant from trial intervention and treatment, sites should explain the importance of remaining on trial follow-up, or failing this, of allowing routine follow-up data to be used for trial purposes. Follow-up and data collection will continue unless the parent explicitly withdraws consent for follow-up or data collection. Research data obtained up to the point of withdrawal of consent will be retained, and further data will only be collected where required by law for reporting to regulatory agencies (i.e. serious adverse events). Research samples will be destroyed or retained for the purpose of the trial according to the wishes of the parent.

8.7.2.2 Withdrawal from Trial Completely

Parents are free to withdraw consent at any time without providing a reason. Parents who wish to withdraw consent for the trial completely (trial intervention, follow-up and data collection) will be informed that pseudo-anonymised data collected up to the point of that withdrawal of consent will be included in the analyses, in accordance with current data protection legislation. The participant will not contribute further data to the trial (with the exception of serious adverse event data); the CTRC should be informed in writing and a Withdrawal CRF should be completed. Data up to the time of withdrawal will be included in the analyses.

